first dose at the study center would complicate the administration of the second dose 12 hours later (e.g. first dose at 3 p.m. will require second dose at 3 a.m.), the subject can self-administer both doses at home to allow for a more convenient dosing schedule (e.g., 8 p.m. and 8 a.m.). Subjects will record study drug dosing details in their study diary.

Assessment of Clinical Cure (TOC [Day 11 ±3])

At the TOC visit (Day 8-Day 14), subjects will return any remaining medication as well as empty bottles of the study drug and treatment compliance will be evaluated. Subject diaries will be returned and reviewed. The investigators and the subjects will rate the signs and symptoms of infection, respectively, on the VSS Scale. A vaginal sample for fungal culture and for species identification and antifungal susceptibility testing will be obtained and sent to a designated central laboratory. An abbreviated physical exam, vital signs measurements and safety laboratory tests will also be performed.

If the baseline vulvovaginal symptoms have not noticeably improved or have worsened and the investigator considers that rescue antifungal medication may be needed, a vaginal sample should also be obtained for KOH testing by the local laboratory.

Follow up (Day 25 [±4])

At the FU visit, subjects will rate their symptoms of infection on the VSS Scale. Vulvovaginal samples for KOH testing and fungal culture should be obtained if there is persistence or recurrence of vulvovaginal symptoms. Only if symptoms are present, the investigator will perform a vulvovaginal examination to rate the subject's signs of infection.

All Visits

AEs and prior/concomitant medications will be assessed and documented at all visits.

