10.1.2 Study Assessments

The study will include efficacy, safety and tolerability assessments.

Efficacy Assessments

The primary efficacy endpoint of the study is the percentage of subjects with clinical cure (complete resolution of signs and symptoms) at the TOC visit. Secondary efficacy endpoints include the percentage of subjects with mycological eradication (negative culture for growth of *Candida* species) at the TOC visit, the percentage of subjects with clinical cure and mycological

eradication at the TOC visit, the percentage of subjects with complete resolution of symptoms at the FU visit, and the percentage of subjects with clinical improvement (partial or complete resolution of signs and symptoms with a total composite score no greater than 1) at the TOC visit and the absolute change in signs and symptoms score from Baseline to TOC and FU visits..

Clinical Evaluation

The signs (edema, erythema and excoriation or fissures) and symptoms (burning, itching and irritation) of infection will be assessed by the investigator and the subject, respectively, on the VSS Scale [provided in [Appendix B](#)]). The VSS Scale is a standardized, predefined scale where each sign and symptom will be given a numerical rating based on severity (absent = 0; mild = 1; moderate = 2; severe = 3) to calculate a total composite score.

Mycological Testing

Mycological tests will include direct microscopic examination with 10% KOH and fungal cultures. KOH will be performed locally at Screening for the determination of subject eligibility and at the TOC visit or FU visit if symptoms persist or recur. Vaginal samples will be collected at Screening, TOC visit and when possible vaginal samples will also be collected prior to the initiation of rescue antifungal medication during the study for central lab fungal cultures. The central lab will culture samples for the presences of yeast, and process isolates for species identification and susceptibility testing.

Safety Assessments

Safety procedures will include collection of AEs, treatment discontinuations, physical examination, vital signs, safety laboratory tests and prior and concomitant medications.

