14.10 Vulvovaginal Samples for KOH and Fungal Culture

At Screening, a vulvovaginal specimen will be obtained for direct microscopic examination with 10% KOH. Subjects must have a positive KOH test at Screening to be randomized to one of the study treatment groups. The Screening KOH will be assessed at the site by the investigator or qualified designee. A vaginal sample will also be obtained at Screening and at the TOC visit for fungal culture and species identification by the central laboratory and for susceptibility testing against ibrexafungerp and additional antifungal agents (per CLSI M27-A3 guidelines). If there is persistence or recurrence of vulvovaginal symptoms, additional vulvovaginal specimens will be collected for KOH testing at the TOC and at the FU visits, and for fungal culture at the FU visit. Samples will also be obtained at any unscheduled visit, if needed.

If the subject experiences persistence or worsening or recurrence of symptoms that per the investigator's assessment (e.g. symptoms ≥ 3) warrant the use of rescue antifungal therapy, a vaginal examination with collection of samples for KOH (assess at the site) and culture should be completed prior to initiation of rescue therapy. If the KOH test is negative, the investigator should consider other causes for the persistence or worsening of the symptoms and antifungal rescue medication may not be indicated. If the collection of the vaginal culture is not possible prior to the initiation of the rescue therapy, it should still be collected as soon as possible after rescue therapy is given.

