15.0 Study Schedule

Detailed schedules of all study visits and procedures are presented in Schedule of Visits and Procedures (Table 1).

Table 1: Schedule of Visits and Procedures (Study SCY-078-303)

Visit	V1 Screening ^a	V2 Baseline ^a	V3 TOC	V4 Follow-up	Unscheduled Visits
Day (allowable window)	D-1 (-2)	D1	D11 (±3)	D25 (± 4)	
Study Procedures					
Informed consent ^b	X				
Assignment of Subject ID number	X				
Inclusion/exclusion criteria	X	X			
Medical history and demographics	X				
Abbreviated physical exam	X		X		If needed
Urine pregnancy test ^c	X				If needed
Safety labs ^d	X		X		If needed
Rating of vulvovaginal symptoms by the subject ^e	X	X-----X		X	If needed
Vulvovaginal sample for other pathogens and pH ^e	X		If symptoms	If symptoms	If needed
Vulvovaginal sample for KOH ^e	X		If symptoms	If symptoms	If needed
Vulvovaginal sample for fungal culture ^e	X		X	If symptoms	If needed

Visit	V1 Screening ^a	V2 Baseline ^a	V3 TOC	V4 Follow-up	Unscheduled Visits
Day (allowable window)	D-1 (-2)	D1	D11 (±3)	D25 (± 4)	
Study Procedures					
Rating of vulvovaginal signs by the investigator ^e	X		X	If symptoms ^f	If needed
Randomization		X			
Study drug and subject diary ^g dispensing		X			
Study drug dosing ^h		X			
Subject diary completion		X-----X			
Study drug collection and treatment compliance evaluation			X		
Subject diary collection and review			X		
Vital Signs	X		X		If needed
Prior & concomitant medication review	X	X	X	X	X
AE monitoring	X	X	X	X	X

Abbreviations: AE=adverse event; D=day; TOC=test of cure; V=visit

- a. Screening and Baseline may occur on the same day.
- b. For subjects under the legal age of consent, the subject’s parent or legal representative will also sign the subject’s ICF.
- c. Results should be reviewed prior to randomization at Baseline (Day 1).
- d. Hematology and blood chemistry. Safety laboratory tests will be performed by a qualified central laboratory.
- e. If the subject experiences persistence or worsening or recurrence of symptoms, after the baseline visit, that per the investigator’s assessment (e.g. symptoms ≥3) warrant the use of rescue antifungal therapy, the symptoms that led to the use of rescue antifungal therapy must be documented in the eCRF and a vaginal examination with rating of signs by the investigator should be completed. Additionally, vulvovaginal samples should be obtained for KOH testing

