4.4. Handing of missing data

For categorical response endpoints including clinical outcome, mycological outcome, symptom outcome, and clinical improvement, subjects will be considered a non-responder for the non-responder imputation (NRI) analysis if they do not meet the clinical response criteria for categorical responses or are missing categorical response data at the specific visit. Randomized subjects without at least 1 post-baseline observation will also be defined as non-responder for the NRI analysis such that subjects who have a missing value at the TOC visit or FU visit will be assigned as treatment failures, i.e., non-responders or positive mycological outcome for the corresponding visit. Randomized subjects without study treatment will be excluded from all analysis.

5. Subject Disposition

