8.2. Secondary Efficacy Endpoints

8.2.1. Mycological outcomes

The percentage of subjects with mycological eradication (negative culture for growth of *Candida* species) at the TOC visit will be analyzed by *Candida* Species of the baseline yeast and overall, using the same inferential analysis employing the same methods as for the primary analysis as noted in Section 8.1.1. The subjects with missing TOC visit data for the mycological outcome will be imputed as mycological persistence using the NRI method described in Section 4.4.

Mycological outcomes will be assessed at the specified visit according to the following definitions.

- Mycological Eradication: A subject with negative culture for *Candida* species without need for further antifungal treatment prior to the TOC visit;
- Mycological Persistence: A subject with a positive culture for *Candida* species or use of additional vulvovaginal or systemic antifungal therapy prior to the TOC visit. For the subject who early terminated before TOC visit and received additional vulvovaginal or systemic antifungal therapy prior to the early termination visit, the subject is considered a mycological persistence.

In addition, a sensitivity analysis will be conducted based on the mITT set where subjects with the imputed mycological outcome using the NRI method at the TOC visit will be removed from the analysis.

The same analysis will be done for the percentage of subjects with mycological eradication (negative culture for growth of *Candida* species) at the FU visit.

The change of mycological outcomes will be summarized in shift tables comparing the testing results at TOC visit with those at FU visit.

The analyses for mycological outcome will only be conducted for the mITT and PP sets.

In addition, a summary table will be presented to include CLSI MIC range, mode, MIC50, and MIC90, based on the ITT and mITT sets by treatment group for the following MIC results:

- MIC results for SCY-078 and fluconazole (FLU) at 24 hours against candida species isolates obtained at TOC visit;
- MIC results for SCY-078 at 48 hours against candida species isolates obtained at TOC visit.

Frequency cross-tabulations of mycological persistence at baseline versus mycological eradication at TOC visit will be presented by treatment group by candida species isolates obtained at baseline.

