8.2.3. Symptom Outcome

The percentage of subjects with complete resolution of symptoms at the Follow-up (FU) visit will be analyzed by Candida Species of the baseline yeast and overall, using the same inferential analysis employing the same methods as for the primary analysis as noted in Section 8.1.1. The subjects with missing Follow-Up data for the symptom outcome will be imputed as symptom persistence using the NRI method described in Section 4.4.

Symptom outcomes will be assessed at the FU Visit according to the following definitions:

- Symptom Resolution: All symptoms are absent (score = 0) without need for further antifungal treatment or topical vaginal drug therapy for the treatment of vulvovaginal irritation/pruritus prior to or at FU visit;
- Symptom Persistence: No response to therapy or incomplete resolution of symptoms or use of additional vulvovaginal or systemic antifungal therapy or topical vaginal drug

therapy for the treatment of vulvovaginal irritation/pruritus prior to or at FU visit. For the subject who early terminated before the FU visit and received additional vulvovaginal or systemic antifungal therapy or topical vaginal drug therapy for the treatment of vulvovaginal irritation/pruritus prior to or at the early termination visit, the subject is considered a symptom persistence.

In addition, a sensitivity analysis will be conducted based on the mITT set where the subjects with the imputed symptom outcome using the NRI method at the FU visit will be removed from the analysis.

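### SAP 8.2.1 tests mycological eradication at follow-up, but follow-up cultures are scheduled only for subjects with symptoms

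*SAP*

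**What the plan says.** **Analysis.** SAP 8.2.1 analyses eradication at TOC with the primary-analysis methods of 8.1.1: a Cochran-Mantel-Haenszel (CMH) test with p-value, odds ratio and 95% confidence interval. It adds an mITT sensitivity analysis that removes imputed subjects, then states "The same analysis will be done for the percentage of subjects with mycological eradication" for the FU visit.

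**Imputation.** SAP 4.4 covers mycological outcome and says that subjects with a missing value at the TOC "or FU visit will be assigned as treatment failures, i.e., non-responders or positive mycological outcome for the corresponding visit". The imputation sentence inside 8.2.1 is narrower: "The subjects with missing TOC visit data for the mycological outcome will be imputed as mycological persistence". By contrast, 8.2.3 names the later visit: "The subjects with missing Follow-Up data for the symptom outcome will be imputed as symptom persistence".

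**Data collection.** For the FU visit, Protocol 10.1.1 says: "Vulvovaginal samples for KOH testing and fungal culture should be obtained if there is persistence or recurrence of vulvovaginal symptoms". Protocol 14.10 likewise makes extra specimens conditional on persisting or recurring symptoms, "for KOH testing at the TOC and at the FU visits, and for fungal culture at the FU visit". In Protocol Table 1 and SAP Appendix 1 the row "Vulvovaginal sample for fungal culture" is unconditional at TOC and conditional on symptoms at FU. The mycological testing paragraph of Protocol 10.1.2 lists no routine FU culture: "Vaginal samples will be collected at Screening, TOC visit and when possible vaginal samples will also be collected prior to the initiation" of rescue medication.

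**Related rule.** SAP 8.1 recognises that symptom-free subjects need no FU examination. It treats their unrated signs as not missing and sets the composite score to zero. No such rule exists for cultures.

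**The concern.** The FU analysis needs a culture result from every subject, but the schedule supplies one only for subjects with symptoms. Whether a result exists therefore depends on a post-randomisation outcome that treatment is expected to change.

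If SAP 4.4 applies, a subject who is well at FU and followed the protocol is scored as having persistent *Candida*. The more often an arm clears symptoms, the more of its subjects are scored that way. If SAP 4.4 does not apply, the comparison is confined almost entirely to subjects with symptoms at FU, plus any antifungal users counted as persistence by definition.

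The per-protocol set does not help, because SAP 4.3 requires a vaginal culture at TOC only. At stake are a reported FU p-value and odds ratio that could understate the drug's effect, or show a disadvantage that does not exist.

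**Working it through.** The documents give no figure for FU eradication in this trial, so there is none to reproduce. The sample size (282 evaluable: 94 placebo plus 188 active for 30% vs 50%) does reproduce, with power 0.902, and is not in dispute.

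**Inputs from the documents**
- 366 randomised 2:1, about 20% without a positive baseline culture (SAP 4.1): mITT about 366 × 0.8 = 293, split about 195 and 98.
- Phase 2b, 600-mg arm, n = 27 (Protocol 7.1): 70% with zero signs and symptoms at FU. This motivates 70% for the drug arm. It is a loose proxy: 19/27 is inferred from 70% of 27, and its exact 95% CI is 49.8% to 86.2%.

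**Assumed inputs**
- s = share symptom-free at FU, not cultured by design
- a = share truly culture-negative among them
- e = share rescued by TOC, who have no FU visit (Protocol 11.4), counted as persistence
- q = negative-culture rate among symptomatic subjects, all cultured

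Other missing data and off-schedule cultures are ignored. Rates are crude, not stratified CMH results. Subscripts d and p denote drug and placebo.

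**Formulas**
- True rate = s·a + (1 − s − e)·q
- NRI rate = (1 − s − e)·q, which cannot exceed 1 − s
- Bias in the drug-placebo difference under NRI = −(s_d·a_d − s_p·a_p); q and e cancel

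**Ceiling.** For s of 60% to 80%, the NRI rate cannot exceed 40% to 20%, whatever the drug does.

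**Subjects imputed by design, s_p = 50%**
- s_d = 60%: 117 + 49 = 166 of 293 (57%)
- s_d = 80%: 156 + 49 = 205 of 293 (70%)

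**Bias in percentage points, same a in both arms**

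| s_d / s_p | a = 40% | a = 60% | a = 80% |
|---|---|---|---|
| 60% / 50% | −4 | −6 | −8 |
| 70% / 50% | −8 | −12 | −16 |
| 80% / 50% | −12 | −18 | −24 |

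The placebo share has no source in the documents. With s_d = 70% and a = 60%:
- s_p = 30%: −(0.42 − 0.18) = −24 points
- s_p = 70%: −(0.42 − 0.42) = 0

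With s = 70% / 50% and unequal a (60% vs 40%), the bias is −(0.42 − 0.20) = −22 points.

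**Illustration: s = 70% / 50%, a = 60%, q = 35%**

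| | Drug | Placebo | Difference (points) |
|---|---|---|---|
| No rescue exits: true | 0.42 + 0.105 = 52.5% | 0.30 + 0.175 = 47.5% | +5.0 |
| NRI | 10.5% | 17.5% | −7.0 |
| Observed only | 35% | 35% | 0 |
| Exits 10% / 25%: true | 0.42 + 0.07 = 49.0% | 0.30 + 0.0875 = 38.75% | +10.25 |
| NRI | 7.0% | 8.75% | −1.75 |
| Observed only, exits removed | 35% | 35% | 0 |
| Observed only, exits kept as persistence | 0.07/0.30 = 23.3% | 0.0875/0.50 = 17.5% | +5.8 |

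The NRI bias is −12 points in both cases. The observed-only result depends on how exits are handled and recovers the true difference in neither case.

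**The case against.** **Scope.** FU eradication is not an endpoint in Protocol 9.2 or SAP 3.2.2; it enters through one sentence in SAP 8.2.1. This stands, and it places the point below anything that touches a listed endpoint.

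**The sensitivity analysis.** The 8.2.1 analysis that removes imputed subjects comes directly before the FU sentence and most naturally carries over to FU. Both results would then appear together, and the gap in denominators would show how many subjects were imputed. That lowers the risk of a lone misleading figure. It does not repair the estimate, because the second result is the symptomatic-only comparison.

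**Is NRI meant at FU?** The imputation sentence in 8.2.1 names only TOC, and Protocol 18.6.2 leaves data other than the primary endpoint unimputed. The NRI reading therefore rests on SAP 4.4 together with the repeat-analysis sentence. That is fair, but SAP 4.4 names the FU visit explicitly and the alternative reading fails too.

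**The numbers.** Every s, a, e and q is assumed, and the only 50% FU figure for zero signs and symptoms in Protocol 7.1 belongs to fluconazole. Phase 2b also reported 48% FU eradication at this dose. However, the ceiling implied by the interval for 19/27 runs from 13.8% to 50.2%, so 48% is not excluded, and the documents do not say how Phase 2b collected FU cultures. The scenario values are not an expected bias; the ceiling and the bias formula do not depend on them.

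**Conclusion.** The concern holds. The planned FU eradication analysis conflicts with the culture schedule, and neither reading of the imputation rule estimates FU eradication by randomised arm.

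Under NRI each arm's rate is capped at one minus its symptom-free share. The difference is biased against the drug whenever s_d·a_d exceeds s_p·a_p. At 70% vs 50% symptom-free the bias is −8 to −16 points for a between 40% and 80% in both arms; it turns in the drug's favour only if a_p/a_d exceeds 1.4. Whether the reported difference changes sign is uncertain, since that also depends on culture results in symptomatic subjects and on rescue exits.

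Two drafting gaps belong with this. Neither Protocol 18.4 nor 18.6.2 provides for FU imputation, and SAP section 11 does not list it as a change. The 8.2.1 outcome definitions count antifungal use only before TOC, whereas 8.2.3 counts it up to and including FU.

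This should be fixed before unblinding. The primary endpoint, the listed secondary endpoints and the sample size are unaffected.

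**What to change.** - In SAP 4.4 and 8.2.1, state that an FU culture the protocol does not require is not missing and is not imputed by NRI.
- Delete the inferential FU eradication analysis. Report FU cultures descriptively, with the number cultured in each arm.
- For the TOC-to-FU shift table, state that only observed cultures are used. Add separate rows for subjects not cultured because symptom-free at FU, subjects who exited after rescue, and other missing results.
- For any FU mycological outcome, count antifungal use up to the FU visit, in line with SAP 8.2.3.

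The cost is SAP wording only, with no change to visits or data collection. The sponsor gives up an FU p-value that the collected data cannot support. Keeping an FU comparison would require either a prespecified rule for cultures absent by design, resting on assumptions these data cannot check, or an FU culture from every subject, which changes data collection.

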8.2.2. Overall Outcome

The percentage of subjects with clinical cure and mycological eradication (overall outcome) at the TOC visit will be analyzed by Candida Species of the baseline yeast and overall, using the same inferential analysis employing the same methods as for the primary analysis as noted in Section 8.1.1. The subjects who cannot determine the overall outcome at the TOC visit will be removed from the analysis and no missing data will be imputed for both clinical outcome and mycological outcome.

Overall outcomes will be assessed at the TOC Visit (Day 11) according to the following definitions:

- Overall Success: A subject with the achievement of both a clinical cure and mycological eradication;
- Overall Failure: A subject with either clinical failure or mycological persistence.

The analyses for overall outcome will only be conducted for the mITT and PP sets. The overall outcomes will be listed with baseline species referenced aside in a listing.

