18.4 Handling of Missing Data, Dose Adjustments, and Early Withdrawals

For the efficacy analyses, subjects who do not have a TOC (Day 8-Day 14) assessment will be assigned as treatment failures. For subjects who withdraw from the study early, every effort will be made to collect TOC visit information at the point of withdrawal.

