18.6.2 Efficacy Analyses

The efficacy analyses will be conducted using the mITT (primary analysis population), ITT and PP populations to evaluate ibrexafungerp vs. placebo.

The primary endpoint, percentage of subjects with clinical cure at TOC, will be analyzed using a Cochran Mantel Haenszel (CMH) test adjusted for site; the p-value and 95% confidence intervals will be presented. Missing Day 8-Day 14 (TOC) data for the primary endpoint will be imputed as failures in the analysis. A sensitivity analysis will be performed where subjects with missing values will be removed from the analysis. All other data will be analyzed as is with no imputation.

For other continuous efficacy endpoints, a two-way analysis of variance (ANOVA) model will be used including effects for treatment and site; p-values and 95% confidence intervals will be presented. For other categorical endpoints, the CMH test adjusted for site will be performed, and p-values and 95% confidence intervals will be presented.

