8.1.1. Primary Analysis

The primary efficacy analysis will be performed on the mITT set at the TOC visit and will compare the proportion of subjects, in the treatment and placebo groups, who have a clinical cure at the TOC visit.

The number and percentage of subjects with clinical cure at the TOC visit will be presented by treatment group. A Cochran Mantel Haenszel (CMH) test adjusted for site and diabetes mellitus diagnosis (Yes or No) will be performed to assess the statistical significance of a difference between treatment groups in the primary efficacy analysis. Mathematically stated:

$$\begin{aligned} H_0: \text{TOC Clinical Cure Rate Oral ibrexafungerp 300-mg dose} &= \text{TOC Clinical Cure Rate Placebo} \\ H_1: \text{TOC Clinical Cure Rate Oral ibrexafungerp 300-mg dose} &\neq \text{TOC Clinical Cure Rate Placebo} \end{aligned}$$

The p-value, odds ratio and 95% confidence interval will be presented in the ibrexafungerp 300-mg treatment arm compared to the placebo arm. Missing data for clinical outcome will be imputed using the NRI method described in Section 4.4. Additional summarizations will be performed by Candida Species of the baseline yeast, and the same inferential analysis will be performed, as appropriate.

The same inferential analysis employing the same methods as for the primary analysis will be performed for the ITT set and PP set to assess clinical cure at TOC visit. Missing data for clinical outcome will be imputed using the NRI method described in Section 4.4. No adjustment of type I error will be performed as these analyses are considered supportive to the primary analysis.

A sensitivity analysis using the mITT set will be performed where subjects with the imputed clinical outcome using the NRI method at TOC visit will be removed from the analysis.

Two subgroup analyses will be performed depending on Body Mass Index category ($\leq 35 \text{ kg/m}^2$ or $> 35 \text{ kg/m}^2$).

Analysis of time to resolution of signs and symptoms after initiation of study drug will use Kaplan-Meier method to estimate the median resolution time and its 2-sided 95% confidence intervals (CIs) based on the ITT, mITT, and PP sets. The time to resolution of signs and symptoms after initiation of study drug is defined as time (days) from first dose of study medication to the first resolution of signs and symptoms. Subjects who discontinued early will be censored at the last available assessment.

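### The responder endpoint drops mITT subjects with an undetermined outcome, while its two components and every other binary secondary endpoint count missing data as failure

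*SAP*

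**What the plan says.** SAP 8.2.2 (Overall Outcome) analyses the responder endpoint in the mITT and PP sets. Subjects whose overall outcome cannot be determined at TOC "will be removed from the analysis and no missing data will be imputed for both clinical outcome and mycological outcome". No NRI version and no sensitivity analysis follow. The same section says that the inferential methods are those of the primary analysis, and it gives this definition: "Overall Failure: A subject with either clinical failure or mycological persistence".

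The SAP treats the other binary efficacy endpoints differently. For clinical cure, SAP 8.1.1 states: "Missing data for clinical outcome will be imputed using the NRI method described in Section 4.4". In SAP 8.2.1 a missing culture result is "imputed as mycological persistence using the NRI method". In SAP 8.2.3 missing follow-up symptoms are "imputed as symptom persistence using the NRI method described in Section 4.4". SAP 8.2.4 does the same for clinical improvement. The general rule in SAP 4.4 opens with "For categorical response endpoints including clinical outcome, mycological outcome, symptom outcome, and clinical improvement" and does not name the overall outcome.

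The protocol points both ways. Section 18.4: "For the efficacy analyses, subjects who do not have a TOC (Day 8-Day 14) assessment will be assigned as treatment failures". Section 18.6.2, after imputing failure for the primary endpoint: "All other data will be analyzed as is with no imputation". SAP section 11, which lists the changes from the protocol, mentions no missing-data rule.

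**The concern.** The responder outcome is the conjunction of two outcomes, so responders should be a subset of the clinically cured. Under the plan, a subject with no TOC data is scored as a failure on cure and as a failure on eradication. Either failure makes an Overall Failure by the SAP's own definition, yet the subject is left out of the responder analysis. The main responder rate then rests on a smaller denominator than the main rates of its components, and its level is higher than under the rule used for them.

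The removal is also not neutral with respect to outcome. One known failing component is enough to classify a subject, so a subject who lacks only the culture stays in if she is a clinical failure and is removed if she is cured.

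At stake are the level and, if missingness differs by arm, the treatment comparison of a named secondary endpoint. The PP set already requires TOC signs, symptoms and a collected culture, so this is essentially an mITT matter.

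**Working it through.** **1. The rules side by side**

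| Endpoint | SAP | Main rule for missing data | mITT sensitivity analysis |
|---|---|---|---|
| Clinical cure, TOC | 8.1.1 | NRI | removal |
| Mycological eradication, TOC | 8.2.1 | NRI | removal |
| Responder (overall) outcome, TOC | 8.2.2 | removal | none |
| Symptom resolution, FU | 8.2.3 | NRI | removal |
| Clinical improvement, TOC | 8.2.4 | NRI | removal |

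**2. Size of the mITT set.** The documents give no sample-size figure for the responder endpoint. Their figure for clinical cure reproduces: 50% against 30%, 2:1, two-sided 5%, 90% power and an uncorrected chi-squared test give 94 + 188 = 282 (power 90.2%). With 366 randomized and 20% expected to be culture-negative at baseline, the mITT set is about 0.8 × 366 = 292.8 subjects, or 195 and 98 by arm (0.8 × 244 and 0.8 × 122).

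**3. Both components missing.** Let c be the cure rate, e the share of cures that are also eradicated, and m the undetermined share, equal in both arms. The value of m is an assumption; the documents give 10% early withdrawal, which is not the same quantity.

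- Planned responder rate: c·e
- NRI responder rate: c·e·(1−m)
- Ratio, planned to NRI: 1/(1−m) = 1.053, 1.111, 1.176 at m = 5%, 10%, 15%
- Subjects removed: 292.8·m = 14.6, 29.3, 43.9

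At m = 10%, e = 95% and c = 50%/30%, the planned rates are 47.5%/28.5% (difference 19.0 points). The NRI rates are 42.8%/25.7% (difference 17.1 points).

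**4. Can the responder rate exceed the cure rate?** The NRI cure rate is c·(1−m), so the planned responder rate exceeds it only if e > 1−m. At m = 10% the NRI cure rates are 45%/27%:

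| e | Planned responder rate | Against NRI cure rate |
|---|---|---|
| 95% | 47.5%/28.5% | above |
| 90% | 45.0%/27.0% | equal |
| 80% | 40.0%/24.0% | below |

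At m = 5%, e = 95% gives equality. The documents give no joint rate. In the Phase 2b 600-mg arm (Protocol 7.1), 14 of 27 were cured and 63%, about 17, were eradicated. The joint count therefore lies between 14 + 17 − 27 = 4 and 14, and e between 4/14 = 29% and 100%. Inversion is possible but not shown.

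**5. Only the culture missing, in a fraction u.** Only cured subjects are then removed, a share c·u of the arm.

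- Planned rate: c(1−u)e / (1−c·u)
- NRI rate: c(1−u)e

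At u = 10% and e = 95%, 5.0% of the drug arm and 3.0% of the placebo arm are removed. The planned rates are 0.4275/0.95 = 45.0% and 0.2565/0.97 = 26.4%. NRI gives 42.8%/25.7%, and complete data would give 47.5%/28.5%. Here there is no inversion against the 50%/30% cure rates.

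**6. Effect on the test.** Illustration with 195 against 98 subjects, assumed responder rates of 40% against 25% among determined subjects, and an unstratified two-proportion z test in place of the planned CMH test:

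| Undetermined, drug/placebo | Removal | NRI |
|---|---|---|
| 10%/10% | 70/176 v 22/88: 14.8 points, p = 0.018 | 70/195 v 22/98: 13.4 points, p = 0.019 |
| 15%/5% | 66/166 v 23/93: 15.0 points, p = 0.015 | 66/195 v 23/98: 10.4 points, p = 0.068 |
| 5%/15% | 74/185 v 21/83: 14.7 points, p = 0.020 | 74/195 v 21/98: 16.5 points, p = 0.004 |

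**The case against.** The strongest reply is that removal is explicit and has protocol support. Protocol 18.0 makes no imputation the default, and 18.6.2 imputes only the primary endpoint. On that reading SAP 8.2.2 conforms, and the departures missing from section 11 are the NRI rules in 8.2.1, 8.2.3 and 8.2.4. This stands as far as it goes, but 18.4 says the opposite, and the SAP chose NRI everywhere else. Either reading leaves a choice that section 11 should record.

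Second, inversion arises only when a removal rate is set beside an NRI rate. Against the planned removal analysis of clinical cure it cannot occur. This also stands, so inversion is a possible symptom and not the main argument.

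Third, m may well be below 10%. Subjects with one known failing component, including rescue use before TOC, remain as failures. The protocol asks for TOC procedures at early termination, and some early withdrawals come after TOC. That is a fair reason to read the lower end of the range.

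Fourth, if outcomes are missing at random, removal lies closer than NRI to the complete-data rate in both cases worked above, and NRI does not recover a cure that lacks a culture. That is true, but it holds equally for the components, where the SAP accepted NRI. The argument here is for one rule and one denominator, not for NRI as the more accurate estimate.

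Finally, a reader could divide the responders by the mITT size to get the NRI rate. That gives the rate but not a prespecified, stratified comparison.

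**Conclusion.** The concern holds. In the mITT set the responder endpoint follows a different missing-data rule from both of its components and from the other two binary secondary endpoints, and it has no companion analysis under their rule. The protocol does not settle which rule applies.

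The certain effect is on level: a factor of 1/(1−m) relative to NRI, with m assumed. The effect on the treatment comparison is negligible if missingness is equal between arms. If it is unequal, the comparison can move in either direction, and in one assumed scenario the result crosses 0.05. The documents do not give missingness by arm, so no direction of bias can be claimed. The primary analysis is untouched and the PP analysis nearly so. This is an inconsistency worth correcting before unblinding, not a threat to the main conclusion.

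**What to change.** - In SAP 8.2.2, replace the removal rule with wording such as: *mITT subjects with an undeterminable overall outcome at TOC count as Overall Failure (NRI, full mITT denominator); a sensitivity analysis in the mITT set leaves them out.*
- In SAP 4.4, add the overall outcome to the endpoints covered by NRI.
- In SAP section 11, state how Protocol 18.4 and 18.6.2 are reconciled for the secondary binary endpoints.

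The cost is three or four sentences and one extra table. The planned removal analysis is kept as the sensitivity analysis. Reported responder rates become somewhat less favourable: in the equal-missingness case of step 3, the difference between arms falls from 19.0 to 17.1 points.
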